8.1.2.2.1. Prior to Administration of Study Drugs

During screening, all AEs and SAEs (regardless of relatedness to protocol procedures) are collected after the patient has signed the ICF. For patients who do not enroll in the study (that is, have not received at least 1 dose of LY2510924 or durvalumab), only AEs and SAEs related to protocol procedures are required to be collected.

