10.4. Safety Analyses

All patients who receive at least 1 dose of either study drug will be evaluated for safety and toxicity. AE terms and severity grades will be assigned by the investigator using CTCAE, version 4.03).

Safety analyses will include summaries of the following:

- AEs, including severity and possible relationship to study drug, and concomitant medications
- dose adjustments
- laboratory values
- vital signs and physical examinations
- DLTs at each dose level
- ECGs

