## 6.2. Handling of Dropouts or Missing Data

Missing data, except dates, will not be imputed. Historical data such as historical diagnosis, historical illness, pre-existing conditions and prior therapies should be collected in a sufficiently informative way. For example, in order to be considered as a historical illness, events occurring in the same year as study entry should have at least known month and year for the end date, while events occurring in previous years should have at least a known year for the end date; all previous treatments for cancer should have at least known date, month, and year for the end date, in order to determine if inclusion criteria is met. When dates need to be imputed, missing days will be replaced with 15th of the month and missing day/month with 01 JULY.

Patients who withdraw from the study before receiving study drug will be replaced and will not be included in the safety or efficacy assessments unless the withdrawal is due to a safety issue that is possibly related to study procedure.

In the following situations, patients will be considered DLT-evaluable; otherwise, patients are considered DLT nonevaluable and may be replaced to ensure that enough patients complete one cycle of therapy at each dose level, unless accrual to that cohort has stopped due to a DLT:

1. Completed the DLT observation period (Cycle 1) and received the scheduled durvalumab dose and at least 75% of LY2510924 doses in Cycle 1;
2. discontinued study treatment or study participation before completing Cycle 1 due to a DLT.

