## 6.3. Population for Analysis

Safety and efficacy analyses will be conducted on all patients who have received at least one dose of the study treatment(s), regardless of whether they are deemed evaluable for the assessment of a dose level.

Pharmacokinetic (PK) analyses will be conducted on patients who have received at least one dose of the study treatment(s) and have sufficient samples collected to allow the estimation of LY2510924 and MEDI4736 PK parameters.

Pharmacodynamic (PD) analyses will be conducted on subjects who have received at least one dose of the study treatment(s) and have sufficient samples collected to allow the assessment of PD.

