## 6.8. Safety Analyses

All patients who receive at least one dose of LY2510924 or durvalumumab will be evaluated for safety and toxicity. The National Cancer Institute Common Terminology Criteria for Adverse Events Version 4.0 (NCI-CTCAE v4.0) will serve as the reference document for choosing appropriate terminology for, and grading the severity of, all adverse events (AEs) and other symptoms.

Safety analyses will include summaries of the following:

- adverse events, including severity and possible relationship to study drug
- DLTs at each dose level
- dose adjustments
- laboratory values
- vital signs
- ECG readings
- transfusions

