#### **6.13.1. Efficacy Analysis Variables (RECIST v.1.1)**

Definition of efficacy analysis variables are listed alphabetically.

**Disease Control Rate** is defined as the proportion of treated patients achieving a best overall response of complete response (CR), partial response (PR), or stable disease (SD) per RECIST v.1.1. Patients who do not have any postbaseline tumor response assessments for any reason are considered non-responders and are included in the denominator when calculating the response rate.

**Note.** Best overall response is the best response recorded from the start of treatment until disease progression, in the order of CR, PR, SD, PD, and NE.

**Duration of Response** is defined from the date of first documented CR or PR that is subsequently confirmed (responder) to the date of objective progression or the date of death due to any cause, whichever is earlier. If a responder is not known to have died or have objective progression, then the patient will be censored at the date of last evaluable tumor assessment.

**Objective response rate** is defined as the proportion of treated patients achieving a best overall response of PR or CR per RECIST v.1.1. Patients who do not have any postbaseline tumor response assessments for any reason are considered non-evaluable and are included in the denominator when calculating the response rate.

**Overall survival** is defined as time from the date of first treatment to the date of death from any cause. For each patient who is not known to have died as of the data-inclusion cut-off date for a particular analysis, OS will be censored for that analysis at the date of last contact prior to the data-inclusion cut-off date (contacts considered in the determination of last contact date include AE date, lesion assessment date, visit date, and last known alive date).

**Progression-free survival** is defined as the time from the date of first treatment until the date of radiographic documentation of progression (as defined by RECIST v. 1.1) based on investigator assessment or the date of death due to any cause, whichever is earlier.

**Time-to-response** is the time from the date of first study treatment until the first evidence of a confirmed CR or PR.

[Table CXAD.6.2](#) lists rules for determining date of progression or censor for PFS. The censoring is taken in the following order:

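### SAP 6.2 admits some never-dosed patients to the safety and efficacy assessments, contradicting the at-least-one-dose rule in SAP 6.3 and 6.8 and protocol 10.4

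*SAP*

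**What the plan says.** SAP 6.2 (Handling of Dropouts or Missing Data) deals with patients who never start treatment: "Patients who withdraw from the study before receiving study drug will be replaced". It then says that they "will not be included in the safety or efficacy assessments unless the withdrawal is due to a safety issue that is possibly related" to a study procedure. The exception covers efficacy as well as safety.

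The other population rules require dosing:

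- SAP 6.3: "Safety and efficacy analyses will be conducted on all patients who have received at least one dose of the study treatment(s"), with no exception stated.
- SAP 6.8: "All patients who receive at least one dose of LY2510924 or durvalumumab will be evaluated for safety and toxicity".
- Protocol 10.4: "All patients who receive at least 1 dose of either study drug will be evaluated for safety and toxicity".
- SAP 6.13.1: the objective response rate "is defined as the proportion of treated patients achieving a best overall response of PR or CR per RECIST v.1.1"; DCR also uses treated patients.
- Protocol 10.9: ORR and DCR are divided by the number of enrolled patients. Protocol section 4 and SAP Table CXAD.6.1 both define an enrolled patient as one who has received at least one dose.

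Protocol 8.1.2.2.1 adds that for patients who do not enroll, "only AEs and SAEs related to protocol procedures are required to be collected".

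**The concern.** The exception can apply only to a patient who has had no study drug. By the SAP's own definitions, such a patient cannot contribute to most of what is analysed. A treatment-emergent event must begin or worsen on or after the first dose (SAP 6.8.3). PFS and OS run from first treatment (SAP 6.13.1). Relative study day and baseline are tied to the first dose (SAP Table CXAD.6.1).

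Safety is the primary objective of the expansion arms, so the conflict affects the denominator of the primary tables. SAP 6.8.2 also summarises DLTs and DLT-equivalent toxicities for the safety population, and membership of that population depends on whether 6.2 or 6.3 governs. Because these patients are replaced, they would come on top of the roughly 15 dosed patients per arm. Two programmers following different sections of the same SAP would produce different tables.

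The event is possible. Tumor tissue is an entry requirement, and a new core or excisional biopsy is one way to meet it (protocol 6.1.2, criterion 9).

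**Working it through.** **Inputs.** About 15 dosed patients per expansion arm and exact (Clopper-Pearson) 95% intervals (SAP 5.1 and Table CXAD.5.1). The number of undosed patients who meet the exception, k, is not in the documents. I assume k = 1, 2 or 3 per arm and show the range.

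**Step 1: reproduce the plan's own figures.** For x cases in n, the lower limit is the 0.025 quantile of Beta(x, n − x + 1), taken as 0 when x = 0. The upper limit is the 0.975 quantile of Beta(x + 1, n − x). With n = 15:

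| x | Rate | Computed limits | SAP table |
|---|---|---|---|
| 0 | 0.0 | 0.000–0.218 | 0.0–0.22 |
| 3 | 0.2 | 0.0433–0.4809 | 0.04–0.48 |
| 6 | 0.4 | 0.1634–0.6771 | 0.16–0.68 |
| 9 | 0.6 | 0.3229–0.8366 | 0.32–0.84 |

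The table reproduces to two decimals.

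**Step 2: apply the exception to the safety denominator.** An undosed patient cannot have a treatment-emergent event, so such a rate becomes x/(15 + k). A rate that counts any AE or SAE, treatment-emergent or not, becomes (x + k)/(15 + k) if each added patient's qualifying event falls in the category counted. With x = 3, starting from 3/15 = 20.0%:

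| k (assumed) | Treatment-emergent rate, 3/(15 + k) | Exact 95% CI | All-event or SAE rate, (3 + k)/(15 + k) | Exact 95% CI |
|---|---|---|---|---|
| 1 | 3/16 = 18.8% | 0.0405–0.4565 | 4/16 = 25.0% | 0.0727–0.5238 |
| 2 | 3/17 = 17.6% | 0.0380–0.4343 | 5/17 = 29.4% | 0.1031–0.5596 |
| 3 | 3/18 = 16.7% | 0.0358–0.4142 | 6/18 = 33.3% | 0.1334–0.5901 |

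The treatment-emergent rate is multiplied by 15/16 = 0.938, 15/17 = 0.882 or 15/18 = 0.833. A zero rate stays zero, but with k = 1 its upper limit falls from 0.218 to 0.206 although no exposure has been added. The SAE column is relevant because SAP 6.17 counts an event as serious whether or not it is treatment-emergent.

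**Step 3: check the other quantities.**

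- ORR and DCR: no change if the treated or enrolled definitions in SAP 6.13.1 and protocol 10.9 govern.
- PFS and OS: undefined, since there is no date of first treatment. Even the censoring rule for patients without post-baseline assessments (SAP Table CXAD.6.2) uses that date.
- PK and PD: no change, because SAP 6.3 requires a dose for both sets.
- DLT evaluability for escalation: no change, because SAP 6.2 requires Cycle 1 dosing or discontinuation for a DLT.

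**Step 4: patients without an arm.** The sponsor confirms the cohort or arm only once eligibility is confirmed (SAP 5.2). A patient lost before then has no arm and could appear only in the overall column. With about 45 patients, one addition multiplies a treatment-emergent rate by 45/46 = 0.978.

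**The case against.** The best defence is that the exception exists so that procedure-related harm is not lost. Protocol 8.1.2.2.1 requires those events to be collected in patients who are never dosed, and SAP 6.4 already reports the AE when it is the reason for discontinuation, for all entered patients. On that view the sentence in 6.2 is a loosely worded reporting rule, and the specific definitions elsewhere would prevail. The purpose is credible for safety. It does not explain why efficacy is named, and no text says that 6.3 overrides 6.2.

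It can also be said that few patients would qualify. A fresh biopsy is not always needed, since a recent or archived specimen can serve, and the mandatory on-treatment biopsy in the ovarian arm falls in Cycle 2, after dosing. The shift from 20.0% to 18.8% is small beside an interval of about 4% to 48%. No p-values are planned, and SAP 5.1 says that the tabulated rates are not a basis for decisions. All of this stands, and it limits the size of the problem.

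A reader might infer that the exception dilutes every rate or biases every incidence downward. The documents do not support that. ORR and DCR have their own dosed denominators, zero rates do not move, PFS and OS become undefined rather than diluted, and a rate that counts the qualifying event rises.

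A reader might also infer that the Phase 1b one-third review could be missed, with 5/15 = 33.3% becoming 5/16 = 31.3%. That does not follow either. The rule in SAP 6.15 and protocol 10.10 concerns toxicity during Cycle 1 with a minimum number enrolled, and an undosed patient has no Cycle 1 and is not enrolled.

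**Conclusion.** The conflict is real. It lies in current SAP text and is a stated rule that gives a wrong denominator if followed. SAP 6.2 places some never-dosed patients in the safety and efficacy assessments, while SAP 6.3 and 6.8 and protocol 10.4 exclude them, as do the ORR and DCR definitions.

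If 6.2 were followed, treatment-emergent rates would fall by a relative 6% to 17% for one to three such patients added to 15, and all-event or SAE rates that include the procedure event would rise. Both could happen in the same arm. These sizes rest on an assumed count and on the patients having been assigned to an arm. The likely practical effect is small, because the analyses are descriptive and few patients are likely to qualify. The point is still worth settling, because it concerns the denominator of the primary safety tables.

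**What to change.** Delete the *unless* clause from SAP 6.2. Define the safety and efficacy populations once, in SAP 6.3, as patients with at least one dose, and have 6.2 refer to that definition. Add a separate listing, outside those denominators, of procedure-related AEs and SAEs in undosed patients, using the data already collected under protocol 8.1.2.2.1. No safety information is lost. The cost is one sentence in the SAP and one listing, with no new data collection.

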7.2.2.1. Dose-Limiting Toxicity Determination and Maximum-Tolerated Dose Definition

A DLT is defined as 1 of the following AEs reported during the Phase 1a DLT observation period, if considered to be definitely, probably, or possibly related to either study regimen by the investigator; and fulfills any 1 of the following criterion using National Cancer Institute (NCI) CTCAE version (v) 4.03:

1. Non-laboratory abnormalities (clinical toxicity):
 - a. Any Grade 4 immune-related AE ([Attachment 10](#))
 - b. Any Grade 4 non-laboratory AE
 - c. Any CTCAE Grade ≥ 3 QT prolongation AE
 - d. Any \geq Grade 3 colitis or noninfectious pneumonitis irrespective of duration
 - e. Any Grade 3 immune-related AE (excluding colitis, QT prolongation, or pneumonitis) ([Attachment 10](#)) that does not downgrade to Grade 2 within 3 days after onset of the event despite optimal medical management including systemic corticosteroids, or does not downgrade to \leq Grade 1 or baseline within 14 days
 - f. Any Grade 2 pneumonitis that does not resolve to \leq Grade 1 within 3 days of the initiation of maximal supportive care, including corticosteroid therapy
 - g. Grade 3 toxicity lasting an extended period of time despite optimal supportive care (for example, nausea, vomiting, and diarrhea lasting >3 days; fatigue lasting >7 days)
2. Laboratory abnormalities:
 - a. Any Grade 3 laboratory value if:
 - i. Medical intervention is required to treat the patient, or
 - ii. Associated with clinically significant symptoms. Examples include but are not limited to, \geq Grade 3 thrombocytopenia if associated with bleeding and requires platelet transfusion, \geq Grade 3 febrile neutropenia, or
 - iii. The abnormality persists for >7 days (excluding amylase and lipase)
 - b. Any Grade 4 laboratory abnormalities
 - c. Liver transaminase elevation $>8 \times$ upper limit of normal (ULN) or total bilirubin $>5 \times$ ULN

Note: Liver test abnormality: For HCC patients and patients with liver metastasis who begin treatment with Grade 2 AST or ALT, if AST or ALT increases by 2-fold greater than baseline and lasts for >7 days

- d. ANC >75,000/ μ L or \geq Grade 3 leukocytosis (leukocytes >100,000/ μ L) of any duration, or leukocytosis/granulocytosis causing clinical symptoms
3. Grade 5 toxicity (that is, death)
4. Any other significant toxicity deemed by the primary investigator and Lilly clinical research personnel to be dose limiting, for example:

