The dose levels for dose escalation are provided in [Figure CXAD.6.1](#). The starting dose level will be 20 mg. The 20-mg and 30-mg dose levels will enroll 3 patients initially. The 40-mg dose level will enroll and treat 1 patient initially. After a 2-week observation period, the additional patients will be enrolled after notification from the sponsor. For all dose levels after the initial 3 patients have been enrolled, additional patients (at that dose level) may be enrolled in case of DLT. If deemed necessary, additional dose levels may be explored after discussion between the investigator and the Lilly CRP or designee in consultation with collaborator. The toxicity-band method has the ability to accommodate additional dose levels naturally. The DLT observation period will last for 4 weeks or to the completion of Cycle 1. Additional patients will be enrolled in a cohort to achieve the minimum of 3 evaluable patients if dropouts or dose interruptions occur that result in a patient being nonevaluable for DLTs due to nonmedical reasons. Patients who withdraw from the study during the DLT observation period for reasons other than a DLT may be replaced within the same dose level. For the purpose of making decisions on dose escalation from a safety perspective, patients will be considered evaluable (DLT-evaluable population) if they have either completed the DLT-observation period (Cycle 1) and received the scheduled durvalumab dose and at least 75% of LY2510924 doses in Cycle 1 or have discontinued study treatment or study participation before completing Cycle 1 due to a DLT. If the DLT-observation period is extended to Cycle 2, patients who discontinued during Cycle 2 in the absence of DLT-equivalent toxicity will be considered evaluable for DLT assessment.

Details regarding the toxicity-band method for this study are provided in [Attachment 9](#).

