7.6.3. Evaluable Phase 1a Patients

For Phase 1a, any patient who discontinues from the study for nonmedical reasons before completing the first cycle of study treatment will be deemed nonevaluable for assessment of a dose level and may be replaced within the same dose level, unless they experience a DLT prior to withdrawal. If the patient is noncompliant during Cycle 1 due to reasons other than drug-related toxicity, he or she will be considered nonevaluable and may be replaced. Nonevaluable patients may be replaced to ensure that 3 patients complete 1 cycle of therapy at each dose level, unless accrual to that cohort has stopped due to a DLT. Safety analyses will be conducted on all patients who have received at least 1 dose of study drug, regardless of whether they are deemed evaluable for the assessment of a dose level.

For the purpose of making decisions on dose escalation from a safety perspective, patients will be considered evaluable if:

- they have either completed the DLT observation period (Cycle 1) and
- they have received the scheduled durvalumab dose in the first cycle, and
- they took at least 75% of the cohort-specified doses of LY2510924

OR

- they discontinued study treatment or study participation before completing Cycle 1 due to a DLT

Patients who are not evaluable for PK, but who complete 1 cycle of therapy, may be replaced upon consultation with the investigator(s) and the Lilly CRP or designee to ensure adequate PK data, unless accrual to that cohort has stopped due to a DLT.

8. Safety, Pharmacokinetic, Pharmacodynamic, and Efficacy Data Collection

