Grade 3	Hold study drug/study regimen until resolution to \leq Grade 1 or baseline. For AEs that downgrade to \leq Grade 2 within 7 days or resolve to \leq Grade 1 or baseline within 14 days, resume study drug/study regimen administration. Otherwise, discontinue study drug/study regimen.	Treat accordingly, as per institutional standard.
Grade 4	Discontinue study drug/study regimen (Note: For Grade 4 labs, decision to discontinue should be based on accompanying clinical signs/symptoms, the Investigator's clinical judgment, and consultation with the Sponsor.).	Treat accordingly, as per institutional standard.

Note: As applicable, for early phase studies, the following sentence may be added: "Any event greater than or equal to Grade 2, please discuss with Study Physician."
 AE Adverse event; CTCAE Common Terminology Criteria for Adverse Events; NCI National Cancer Institute.

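### The written DLT-evaluable rule can drop and replace a Phase 1a patient who had a Cycle 1 DLT, and it conflicts with the prose in Protocol 7.6.3

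*SAP*

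**What the plan says.** SAP 6.2 gives two routes to DLT-evaluable status. Route 1 is to finish Cycle 1 having had the durvalumab dose and at least 75% of LY2510924 doses. Route 2 is to discontinue before the end of Cycle 1 because of a DLT. Of all others it says "otherwise, patients are considered DLT nonevaluable and may be replaced to ensure that enough patients complete one cycle of therapy at each dose level", except where accrual to the cohort has stopped for a DLT.

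Protocol 7.2.2.2 uses the same two routes ("received the scheduled durvalumab dose and at least 75% of LY2510924 doses in Cycle 1 or have discontinued study treatment", again early and because of a DLT) and names the result the DLT-evaluable population for escalation decisions. It also lets withdrawals for reasons other than a DLT be replaced, without excepting a patient who already had one. The bullets in Protocol 7.6.3 repeat the dosing condition: "they took at least 75% of the cohort-specified doses of LY2510924".

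The prose above those bullets differs. A nonmedical withdrawal before the end of Cycle 1 is nonevaluable "unless they experience a DLT prior to withdrawal". A patient is also nonevaluable if "noncompliant during Cycle 1 due to reasons other than drug-related toxicity, he or she will be considered nonevaluable", which implies that doses missed because of drug toxicity do not have that effect. Protocol 7.2.2.2 likewise ties the addition of patients to "dropouts or dose interruptions occur that result in a patient being nonevaluable for DLTs due to nonmedical reasons".

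**The concern.** A patient who has had a DLT has already supplied the information that the observation period exists to collect. A minimum-dosing condition is needed only for patients without a DLT, so that a clean Cycle 1 reflects real exposure. The two-route rule applies it to everyone who does not stop because of the DLT.

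The error runs one way. Removing a DLT patient from the evaluable set can only lower its DLT rate. DLTs and the MTD are the Phase 1a primary objective, and the MTD sets the Phase 1b dose.

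**Working it through.** **Step 1: dose threshold.** LY2510924 is given daily for 28 days (Protocol 7.2.1.1). 0.75 × 28 = 21. Missing 7 leaves 21/28 = 75.0%, evaluable. Missing 8 leaves 20/28 = 71.4%, not evaluable.

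**Step 2: DLT patients who fit neither route.**
1. Fewer than 21 doses taken, without discontinuing before the end of Cycle 1 because of the DLT. The 7.6.3 prose conflicts with this only if the doses were missed because of drug-related toxicity. Doses missed for other reasons make the patient nonevaluable under the prose too.
2. Left before completing Cycle 1 for a reason other than the DLT. The 7.6.3 prose expressly keeps this patient if the reason is nonmedical.

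**Step 3: can the missed-dose case arise?** Protocol 7.2.2.1 item 1g makes prolonged Grade 3 toxicity a DLT, with the examples "nausea, vomiting, and diarrhea lasting >3 days; fatigue lasting >7 days". For non-immune Grade 3 events, Attachment 11 holds treatment; if the event settles to Grade 1 or "baseline within 14 days, resume study drug/study regimen administration. Otherwise, discontinue study drug/study regimen". Fatigue of more than 7 days, held from onset and resolved within 14, costs 8 to 14 doses, leaving 20/28 = 71.4% to 14/28 = 50.0%. All 8 fall in Cycle 1 only if the hold starts by Day 21 (Days 21 to 28); a start on Day 22 leaves 21/28 = 75.0%. So the case is possible. It is not certain, because Table CXAD.7.2 pairs restart with a one-level dose reduction, while Protocol 7.2.2 and 7.2.5.1.1 bar reductions in Phase 1a. A patient discontinued for the DLT instead would be evaluable by route 2.

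**Step 4: effect on the model, if it uses the evaluable set.** Inputs from Attachment 9: logit p(d) = α + β·log(d/40). (α, log β) is bivariate normal with means (−1.09, 0.26), SDs (2.17, 0.51) and correlation −0.89. A dose is barred if the posterior P(p > 0.33) exceeds 0.25.

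Check against the plan: numerical integration gives prior medians of 0.052, 0.119, 0.187 and 0.252 at 10, 20, 30 and 40 mg. Table App.1 has 0.06, 0.12, 0.18 and 0.26, so agreement is within 0.01.

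| Data | P(overdose) at | DLT patient kept, n = 3 | Replaced by a DLT-free patient, n = 3 | Kept, DLT-free fourth patient added |
|---|---|---|---|---|
| First cohort, 20 mg | 20 mg | 1/3: 0.380 | 0/3: 0.045 | 1/4: 0.262 |
| 0/3 at 20 mg, then 30 mg | 40 mg | 1/3: 0.296 | 0/3: 0.046 | 1/4: 0.230 |
| 0/3, 0/3, then 40 mg | 40 mg | 2/3: 0.318 | 1/3: 0.100 | 2/4: 0.247 |

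Different integration grids move the third decimal by about 0.002. Kept against replaced crosses 0.25 in all three rows. With four patients counted, only the 20 mg case stays barred; the third row sits just under the limit.

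**Step 5: frequency.** The share f of DLT patients who would be excluded is not in the documents; 5% and 10% are assumed. Table App.3 (mean patients × DLT rate) implies 14.5 × 0.164 = 2.4 to 13.2 × 0.270 = 3.6 DLTs per trial. P(at least one exclusion) = 1 − (1 − rate × f)^n, which is 11% to 16% at f = 5% and 21% to 30% at f = 10%.

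The design was simulated with 10,000 trials per setting, excluded patients replaced and the model followed mechanically. P(40 mg selected) was:

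| Scenario | Table App.3 | f = 0 | f = 5% | f = 10% |
|---|---|---|---|---|
| 1 | 0.689 | 0.691 | 0.713 | 0.734 |
| 2 | 0.546 | 0.522 | 0.550 | 0.580 |
| 3 | 0.374 | 0.373 | 0.401 | 0.431 |
| 4 | 0.222 | 0.230 | 0.254 | 0.279 |

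40 mg is above the true MTD only in Scenario 4.

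**The case against.** The best defence is that no DLT is hidden. Protocol 7.2.2.2 has investigators and sponsor weigh the model, the observed DLT rate and later DLT-equivalent events. Section 10.10 reviews cumulative safety data, Attachment 9 lets the decision depart from the model, and SAP 6.8.2 tabulates DLTs in the safety population. Replacement is optional. All this stands, and a reader who inferred that a DLT could vanish from review would be wrong. It does not settle which patients belong in the set that Protocol 7.2.2.2 defines for escalation.

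Second, the model is described as using observed DLT data; no text says that this means the evaluable set. That also stands, so the figures in Step 4 are conditional.

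Third, it is tempting to say that one exclusion reverses the recommendation at every planned dose. That holds only for keeping the patient in a cohort of three against dropping and replacing. Additional patients may be enrolled after a DLT, and with a DLT-free fourth patient counted the 30 mg and 40 mg examples both allow 40 mg.

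Fourth, the missed-dose example is narrow. It needs a non-immune event, although Attachment 11 treats events without a clear other cause as potentially immune-related, and Protocol 7.2.5 uses discontinuation even for immune-related stops that may resume. It also depends on the unreconciled restart and reduction passages. This lowers the likely frequency. The early nonmedical withdrawal needs none of these conditions.

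**Conclusion.** The counting rule is wrong as written and should be corrected. SAP 6.2, Protocol 7.2.2.2 and the 7.6.3 bullets can make a Cycle 1 DLT patient nonevaluable and replaceable, and the 7.6.3 prose contradicts them for a nonmedical withdrawal after a DLT and, by implication, for doses missed through drug toxicity.

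Two wider readings are not supported. Withdrawal after Cycle 1 is complete, with the required doses taken, leaves the patient evaluable by route 1. And the prose does not rescue a DLT patient who missed doses for reasons unrelated to toxicity.

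In a single trial the effect can be decisive: P(overdose) moves across 0.25 in each kept-against-replaced comparison. This assumes that the evaluable set is the model input and that the replacement has no DLT. On average it is small: 2 to 3 percentage points more selection of 40 mg at f = 5% and 4 to 6 at f = 10%, with f assumed. In Scenarios 1 to 3 the shift is toward the true MTD, so the documents do not show a general drift to overdosing.

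**What to change.** Put one rule in SAP 6.2, Protocol 7.2.2.2 and Protocol 7.6.3, for example:

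> A patient who has a DLT during the DLT observation period is DLT-evaluable and is not replaced, whatever number of doses was taken and whatever the reason for any later discontinuation. A patient with no DLT is evaluable only after finishing the observation period (Cycle 1) with the planned durvalumab dose and 75% or more of the LY2510924 doses.

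Keep the Protocol 7.2.2.2 sentence on extension to Cycle 2. Limit its sentence on replacing withdrawals to patients without a prior DLT. State that the escalation model uses this set. Separately, reconcile Table CXAD.7.2 with the bar on dose reductions in Phase 1a.

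The counting rule changes no dosing or clinical rule. It costs a few sentences in three sections, with no added procedures. The downside is that observed DLT rates may be slightly higher, so the model may hold at a dose a little more often, including where 40 mg is the true MTD.
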